2.2 Secondary estimands

Secondary estimands corresponding to key secondary efficacy endpoints are defined similarly to the primary estimand. These endpoints, and the corresponding summary measures, are listed below. Population, treatment of interest, endpoints, and intercurrent events are defined similarly as for the primary estimand.

- Endpoint: time-adjusted percent change in LDL-C from baseline after Day 90 and up to Day 330 (Year 1). Summary measure: difference between treatment groups in least squares mean time-adjusted percent change in LDL-C from baseline after Day 90 and up to Day 330 (Year 1).
- Endpoint: absolute change in LDL-C from baseline to Day 330 (Year 1). Summary measure: difference between treatment groups in least squares mean absolute change in LDL-C from baseline to Day 330 (Year 1).
- Endpoint: percent change in Apo B from baseline to Day 330 (Year 1). Summary measure: difference between treatment groups in least squares mean percent change in Apo B from baseline to Day 330 (Year 1).
- Endpoint: percent change in Lp(a) from baseline to Day 330 (Year 1). Summary measure: difference between treatment groups in least squares mean percent change in Lp(a) from baseline to Day 330 (Year 1).
- Endpoint: percent change in non-HDL-C from baseline to Day 330 (Year 1). Summary measure: difference between treatment groups in least squares mean percent change in non-HDL-C from baseline to Day 330 (Year 1).
- Endpoint: percent change in total cholesterol from baseline to Day 330 (Year 1). Summary measure: difference between treatment groups in least squares mean percent change in total cholesterol from baseline to Day 330 (Year 1).

3 Study design

This study is a two-part (double-blind, placebo-controlled / open-label) multicenter study in adolescents (aged 12 to <18 years) with HeFH and elevated LDL-C (>130 mg/dL / 3.4 mmol/L) on stable, individualized, optimal SoC background lipid-lowering therapy (including maximally tolerated statin treatment).

The overall study duration is 748 days (excluding a safety follow-up call 30 days after the end of study (EOS) visit).

Following an approximately 4 weeks screening/run-in period, the study has two sequential parts (Figure 3-1).

- **Part 1 (Year 1):** 12 months double-blind, parallel group period in which participants will be randomized to receive either inclisiran sodium 300 mg (equivalent to 284 mg inclisiran^{*}) s.c. or placebo (given at Days 1, 90 and 270).

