5.2 Exclusion criteria

Participants meeting any of the following criteria are not eligible for inclusion in this study.

- 1. Previous treatment (within 90 days of screening) with monoclonal antibodies directed towards PCSK9
- 2. (i) Active liver disease defined as any known current infectious, neoplastic, or metabolic pathology of the liver or (ii) unexplained alanine aminotransferase (ALT), aspartate aminotransferase (AST) elevation >3x ULN, or total bilirubin elevation >2x ULN (except patients with Gilbert's syndrome) at screening confirmed by a repeat measurement at least 1 week apart
- 3. Females who are pregnant or nursing, or who are of child-bearing potential, defined as all women physiologically capable of becoming pregnant (e.g. are menarchal) **unless** they agree to abstinence or, if sexually active, agree to the use of effective methods of contraception during dosing of study treatment. Female participants of child-bearing potential, who are or might become sexually active, must be informed of the need to prevent pregnancy during the study. The effective contraception methods are:
 - Barrier method: Condom or Occlusive cap (e.g. diaphragm or cervical/vault caps). For UK sites only (if applicable): with spermicidal foam/gel/film/cream/ vaginal suppository
 - Use of oral, injected or implanted hormonal methods of contraception or placement of an intrauterine device (IUD) or intrauterine system (IUS) or other forms of hormonal contraception that have comparable efficacy (failure rate <1%), for example hormone vaginal ring or transdermal hormone contraception
 - The decision on the contraceptive method should be reviewed at least every 3 months to evaluate the individual need and compatibility of the method chosen
 - If local regulations deviate from the contraception methods listed above to prevent pregnancy, local regulations apply and will be described in the informed consent form (ICF)
 - Adolescent females who have not reached menarche are exempt from the above requirements; however, to be eligible for inclusion in the study, they must be willing to comply with the above requirements if they gain child-bearing potential during the study
- 4. Any uncontrolled or serious disease, or any medical or surgical condition, that may either interfere with participation in the clinical study, and/or put the participant at significant risk (according to investigator's [or delegate's] judgment) if he/she participates in the clinical study

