6.7.2 Instruction for prescribing and taking study treatment

Investigational and control drugs will not be dispensed to the participants. Study drug injections will be performed exclusively at the study site by qualified clinical study site staff under the supervision of the investigator or designee.

The site of injection is the abdomen, alternating sides for each injection. Injections should not be done into areas of active skin disease or injury such as sunburns, skin rashes, inflammation, tattoos or skin infections.

Participants will be administered one s.c. injection of study drug at pre-defined visits as specified in the Assessment Schedule (Table 8-1) and summarized below.

- **Part 1:** Each participant will receive one injection of blinded inclisiran or placebo on Day 1, a second injection of blinded inclisiran or placebo on Day 90 and a subsequent injection of blinded inclisiran or placebo on Day 270 ("6 months dosing").
- **Part 2:** Participants randomized to placebo in Part 1 will receive a single injection of blinded inclisiran on Day 360, while participants randomized to inclisiran in Part 1 will receive a single injection of blinded placebo on Day 360. All participants will receive subsequent doses of open-label inclisiran on Day 450 and Day 630.

Injections will be administered after all other study assessments have been completed for the visit. At the Randomization (Day 1) and Day 360 visits, vital signs (blood pressure and pulse) and ADA (Day 1 only) will be assessed a second time 4 hours after injection.

Participants must be observed in the clinic for at least 4 hours post injection on Day 1 and Day 360 (i.e. first dosing of inclisiran) and for at least 30 minutes post injection for all other dosing visits before being discharged.

Should a participant develop signs or symptoms of anaphylaxis when study drug is injected, the investigator will need to collect a blood sample for tryptase within 30 minutes of the onset of anaphylaxis (or as soon as possible).

All kits of study treatment assigned by the IRT will be recorded in the IRT system.

All injections to the participant as well as study drug interruptions/discontinuations (i.e. no injection at a designated dosing visit) during the study must be recorded on an appropriate eCRF.

7 Informed consent procedures

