LDL-apheresis recording (if applicable)	x	x	х	x	х	х	х	х	x	х	х	х	
Fasting LDL-C	Х	Х		Х	Х	Х	Х	Х	Х	Х	Х	Х	
Fasting PCSK9		Х		Х	Х		Х	Х		Х		Х	
Full fasting lipid / lipoprotein profile ⁹		Х			х		х	х		х		Х	
Anti-drug antibodies ¹⁰		Х			Х		Х			Х		Х	
Full chemistry ¹¹		Х					Х					Х	
Limited chemistry ¹¹	Х		Х	Х	Х	Х		Х	Х	Х	Х		
Hematology	Х	Х	Х		Х		Х		Х	Х		Х	
Sexual hormones		Х					Х					Х	
Urinalysis	Х	Х	Х		Х		Х		Х	Х		Х	
AEs/SAEs	Х	Х	Х	Х	Х	Х	Х	Х	Х	Х	Х	Х	
Injection site reaction assessment		Х	х	х	х	х	х	х	х	х	x	Х	

Novartis	
Amended Protocol Version 02 (Clean)	

Confidential

Period	Screening ¹		Part 1 (D	ouble-bl	ind, place	bo-contro	lled)		Part 2 (Open-labe	l, single-a	arm)	Follow-up
Visit Name	Screening	Day 1 (Baseline & 1st Treatment)	Day 30	Day 90	Day 150	Day 270	Day 330	Day 360 ("Switch Day") ²		Day 510	Day 630	Day 720 (End of Treatment/ Study) ³	Safety follow-up (last visit +30 days)⁴
Days	-28	1	30	90	150	270	330	360	450	510	630	720	750
Neurological Examination		х					х					Х	
Tanner staging / menarche		х			х		х			х		х	
Safety Follow up Call ¹⁴													S

X Assessment to be recorded in the clinical database or received electronically from a vendor

S Assessment to be recorded in the source documentation only

¹ Screening / run-in period

² Day 360 ("Switch Day") is a shared visit, i.e. the end of Part 1 and the start of Part 2 of the study

³ For participants who prematurely discontinue the study for any reason [e.g. if a participant's parent(s)/legal representative(s) / a participant (if applicable) decide to prematurely and permanently discontinue the participant from study treatment and decline further follow-up visits] an EOS visit should also be scheduled as soon as possible.

⁴ 30 days after the last study visit or 90 days after the last administration of study drug, whatever is longer

⁵ Only in females of child-bearing potential (prior to study treatment administration, if applicable)

⁶ On Day 1 and Day 360 vital signs will be measured prior to injection and 4 hours post injection; at all other visits, vital signs will be measured only once (prior to injection, if applicable).

⁷ Participants will be observed in the clinic for at least 4 hours post injection on Day 1 and Day 360 and for at least 30 minutes post injection for all other dosing visits. ⁸ For any suspected episode of anaphylaxis, the investigator will need to collect a blood sample for tryptase within 30 minutes of an onset of anaphylaxis (or as soon as possible).

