In addition, adolescent females who gain child-bearing potential during the study and are unwilling to comply with the requirements for contraception as outlined in Section 5.2 will be excluded from receiving further study drug.

If discontinuation of study treatment occurs, the investigator should make a reasonable effort to understand the primary reason for the participant's premature discontinuation of study treatment and record this information.

Study treatment may be restarted at the discretion of the investigator, if the reason for discontinuation has resolved. Every effort should be made to restart study treatment, if deemed appropriate by the investigator. Study treatment is **not** allowed to be re-started following initiation of prohibited medication that requires study drug discontinuation (Table 6-2).

Participants who discontinue study treatment or for whom the participant's parent(s)/legal representative(s) / participant (if applicable) decide that they do not to wish the participant to participate in the study further, should NOT be considered withdrawn from the study UNLESS informed consent was withdrawn (see Withdrawal of informed consent, Section 9.1.2). Where **possible, they should return for the assessments indicated** in the Assessment Schedule. If they fail to return for these assessments for unknown reasons, every effort (e.g. telephone, e-mail, letter) should be made to contact the participant's parent(s)/legal representative(s) / participant / pre-designated contact as specified in the lost to follow-up section. This contact should preferably be done according to the study visit schedule.

If the participant cannot or is unwilling to attend any visit(s), the site staff should maintain regular telephone contact with the participant, the participant's parent(s)/legal representative(s) or with another pre-designated person. This telephone contact should preferably be done according to the study visit schedule.

After study treatment discontinuation, at a minimum, in abbreviated visits, the following data should be collected at clinic visits and/or via telephone/email contact:

- New / concomitant treatments
- AEs/SAEs

Where possible, all clinic visit assessments should be performed according to Table 8-1.

The investigator must also contact the IRT to register the participant's discontinuation from study treatment.

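### Menarche is not scheduled at any dosing visit after Day 1, so the protocol does not ensure that newly gained child-bearing potential is recognised before the next dose

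*Protocol*

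**What the plan says.** Exclusion criterion 3 in Protocol 5.2 lists the contraception requirements and then makes an exception: "Adolescent females who have not reached menarche are exempt from the above requirements". The exception is conditional, because such girls are eligible only if "they must be willing to comply with the above requirements if they gain child-bearing potential during the study". Among the listed requirements is a periodic review: "The decision on the contraceptive method should be reviewed at least every 3 months".

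Section 8.4.3 counts a girl as being of child-bearing potential once she becomes menarchal on study. Section 9.1.1 bars from further study drug "adolescent females who gain child-bearing potential during the study and are unwilling to comply with the requirements for contraception".

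In Table 8-1 the row "Tanner staging / menarche" is marked on Days 1, 150, 330, 510 and 720. Study drug in Part 1 is "given at Days 1, 90 and 270" (Section 3). A blinded switch dose follows on Day 360, and then "All participants will receive subsequent doses of open-label inclisiran on Day 450 and Day 630" (6.7.2). The urine pregnancy test is marked on Days 1, 360 and 720. Footnote 5 restricts pregnancy testing: "Only in females of child-bearing potential (prior to study treatment administration, if applicable".

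**The concern.** The exemption, the withholding rule and footnote 5 all depend on whether a girl has reached menarche by the day in question. The only scheduled item that asks about this falls away from every dose after the first. A site that follows Table 8-1 exactly could therefore give an injection on the basis of a status recorded weeks or months earlier.

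The stake is participant protection, not the efficacy analysis. Sections 4.5 and 7 warn that the risk to a fetus is unknown, and 4.2 says the lipid effect of one dose is measurable for more than six months. For a girl randomised to placebo, Day 360 is the first active injection. The duty to start contraception also begins with the change of status, so late recognition delays it for every girl concerned, not only for one who would refuse.

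**Working it through.** **Inputs**, all from Table 8-1 read by column and checked against Sections 3 and 6.7.2:

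- Menarche assessments: Days 1, 150, 330, 510, 720.
- Doses: Days 1, 90, 270, 360, 450, 630.
- Urine pregnancy tests: Days 1, 360, 720.

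**Step 1: overlap.** The dosing days and the menarche days share only Day 1. So 0 of the 5 later dosing visits has a scheduled menarche assessment.

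**Step 2: age of the recorded status at each later dose** (dose day minus day of the last scheduled assessment).

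| Dose | Last assessment | Age in days | Next assessment | Urine test at this visit |
|---|---|---|---|---|
| Day 90 | Day 1 | 90 − 1 = 89 | Day 150 | no |
| Day 270 | Day 150 | 270 − 150 = 120 | Day 330 | no |
| Day 360 | Day 330 | 360 − 330 = 30 | Day 510 | yes |
| Day 450 | Day 330 | 450 − 330 = 120 | Day 510 | no |
| Day 630 | Day 510 | 630 − 510 = 120 | Day 720 | no |

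**Step 3: when the schedule works and when it does not.** Take visits on their nominal days.

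- Menarche on Days 91–150, 271–330 or 451–510 is picked up at a scheduled assessment before the next dose. That is 60 + 60 + 60 = 180 days.
- Menarche on Days 2–90, 151–270, 331–450 or 511–630 is followed by a dose before the next scheduled assessment. That is 89 + 120 + 120 + 120 = 449 days.
- Together these make up the 629 days from Day 2 to Day 630 (180 + 449 = 629).

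These are calendar days, not probabilities. They show where the gap lies, not how many girls fall into it. A girl with menarche on Days 331–360 passes two dosing visits, Days 360 and 450, before the next scheduled question on Day 510.

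**Step 4: which doses are active.** In the inclisiran arm the Day 360 injection is placebo, so the later active doses are on Days 90, 270, 450 and 630, with a recorded status 89, 120, 120 and 120 days old. In the placebo arm the active doses are on Days 360, 450 and 630, at 30, 120 and 120 days.

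**Step 5: the contraceptive review.** Intervals between consecutive visits from Day 1 to Day 720 are 29, 60, 60, 120, 60, 30, 90, 60, 120 and 90 days. Two of them (Days 150–270 and 510–630) are longer than three months, and Table 8-1 has no row for the review.

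**The case against.** The strongest reply is that the exemption depends on a girl's actual status, not on the last eCRF entry. Under 8.4.3 she is of child-bearing potential from menarche, whatever the schedule has recorded. The menarche row serves the pubertal-development endpoint (8.4.4.1), and nothing makes it the only route by which a site may learn of a change. There are other safeguards:

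- Willingness to comply is an entry condition, so the 9.1.1 rule reaches only girls who later refuse.
- Section 4.5 sets a continuing duty: a participant whose compliance is in doubt should not stay in the study.
- Section 8.4.3 allows extra pregnancy tests and asks that menarchal girls and their parents be informed.
- Section 4.5 reports no sign of embryo-fetal harm in the non-clinical studies.

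All of this stands, and it rules out several stronger readings.

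- A reader might infer that the withholding rule cannot act in time. It can: menarche found on Day 150, 330 or 510 is known before the dose that follows, so a post-Day-1 assessment precedes four of the five later doses. Only Day 90 has none.
- A reader might infer that a newly menarchal girl would be passed over by the Day 360 pregnancy test. Footnote 5 points the other way: to apply it before dosing, the site has to establish her status that day.
- A reader might infer that the 120-day visit gaps contradict the three-monthly review. They do not, because 5.2 does not tie the review to a clinic visit. Nor does the review close the gap discussed here, since girls before menarche are exempt from it as written.

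What the reply does not supply is a scheduled step. Asking at other visits is left to the site, extra tests are discretionary, and the Day 360 check is implied and covers one of five doses.

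**Conclusion.** The point holds as a gap in the schedule. None of the five later dosing visits has a scheduled menarche assessment. The last scheduled status is 30 to 120 days old at those doses, and Day 90 has had no check since Day 1. A site can follow Table 8-1 exactly and dose a newly menarchal girl before the change is recorded and before contraception has started. The documents do not show that this will happen, and they do not show that the protective rule is inoperable.

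The conclusion assumes visits on nominal days; real visit dates would shift the gaps slightly. A reader might try to put a number on the girls affected from the 141 enrolled (SAP 1.1). The documents give neither the number of girls nor the share who had not reached menarche at entry. Even that share would count everyone pre-menarchal at entry, not those whose menarche fell between an assessment and a dose and went unrecognised. No figure can be derived. The primary and key secondary analyses are not affected.

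**What to change.** Reconcile Protocol 5.2, 8.4.3, 9.1.1 and Table 8-1 with footnote 5, so that the schedule establishes current child-bearing status relative to each dose and the text says how a change between menarche assessments is identified. How to do this is for the sponsor to decide. One low-burden option is to record menarche status, without Tanner staging, at the existing visits on Days 90, 270, 360, 450 and 630. That would cost one question and one eCRF field at five visits, with no new visit or procedure.

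As a secondary clarification, state how the three-monthly contraceptive review is carried out and documented, given the two 120-day visit intervals and the absence of a row in Table 8-1.

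If dosing is already complete (SAP Amendment 4 is dated 3 December 2024), the recorded menarche dates (8.4.4.1) can be set against the dosing dates to count doses given between menarche and its next scheduled assessment. SAP 2.8.7 already plans a menarche listing, so the cost is one extra cross-listing.

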9.1 Discontinuation and completion

9.1.1 Study treatment discontinuation and study discontinuation

Discontinuation of study treatment for a participant occurs when study treatment is stopped earlier than the protocol planned duration, and can be initiated by either the participant's parent(s)/legal representative(s) / participant (if applicable) or the investigator.

The investigator must discontinue study treatment for a given participant if, he/she believes that continuation would negatively impact the participant's well-being. After study treatment discontinuation, participants should remain in the study and complete other study visit procedures as per the Assessment Schedule, unless consent is withdrawn (Section 9.1.2), preferably in writing.

Study treatment must be discontinued under the following circumstances:

- Participant's parent(s)/legal representative(s) / participant (if applicable) decision
- Pregnancy
- Use of prohibited treatment as per details in the prohibited treatment section (Table 6-2)
- Following emergency unblinding
- Any situation in which study participation might result in a safety risk to the participant
- Severe and persistent (>14 days despite appropriate treatment) reactions at the injection site and any confirmed anaphylactic reactions
- Unexplained increases in transaminases (ALT or AST) or total bilirubin as follows:
 - ALT or AST >5x ULN
 - ALT or AST >3x ULN for more than 2 weeks
 - ALT or AST >3x ULN and (total bilirubin >2x ULN or INR >1.5)
 - ALT or AST >3x ULN with the appearance of fatigue, nausea, vomiting, right upper quadrant pain or tenderness, fever, rash, and/or eosinophilia (>5%)
 - The investigator should evaluate to see if other causes for the laboratory abnormalities are immediately apparent, such as obstructive gall bladder or bile duct disease, viral or alcoholic hepatitis, malignancy involving the liver, congestive hepatopathy, other hepatotoxins or heritable disorders.
- Unexplained C(P)K values >5x ULN confirmed by repeat test when the C(P)K elevation is associated with muscle pain, muscle tenderness and/or muscle weakness, or new onset renal dysfunction
- Any other laboratory abnormalities that, in the judgment of the investigator, prevents the participant from continuing study treatment

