	If normal at baseline: ALT or AST > 3 x ULN If elevated at baseline: ALT or AST > 2 x baseline or > 300 U/L (whichever occurs first)	Total bilirubin > 2 x ULN (or INR > 1.5) For participants with Gilbert's syndrome: Doubling of direct bilirubin	None	 Follow-up for symptoms Initiate close monitoring and workup for competing etiologies Study drug can be restarted only if another etiology is identified and liver enzymes return to
	If normal at baseline: ALT or AST > 3 x ULN If elevated at baseline: ALT or AST > 2 x baseline or > 300 U/L (whichever occurs first)	Normal or elevated	Severe fatigue, nausea, vomiting, right upper quadrant pain	baseline

Criteria	Actions required	Follow-up monitoring		
Total Bilirubin (isolated)				
>1.5 – 3.0 ULN	 Maintain treatment Repeat LFTs within 48-72 hours 	Monitor LFTs weekly until resolutionª to ≤ Grade 1 or to baseline		
> 3 - 10 × ULN (in the absence of known Gilbert syndrome)	 Interrupt treatment Repeat LFT within 48-72 hours Hospitalize if clinically appropriate Establish causality Record the AE and contributing factors (e.g. conmeds, medical history, lab) in the appropriate eCRF(s) 	Monitor LFTs weekly until resolution ^a to ≤ Grade 1 or to baseline (ALT, AST, total bilirubin, albumin, PT/INR, ALP and GGT) Test for hemolysis (e.g. reticulocytes, haptoglobin, unconjugated [indirect] bilirubin)		
> 10 x ULN	 Discontinue the study treatment immediately Hospitalize the participant Establish causality Record the AE and contributing factors(e.g. conmeds, medical history, lab) in the appropriate eCRF(s) 	ALT, AST, total bilirubin, albumin, PT/INR, ALP and GGT until resolution ^a (frequency at investigator discretion)		
Any AE potentially indicative of a liver toxicity	 Consider study treatment interruption or discontinuation Hospitalization if clinically appropriate Establish causality Record the AE and contributing factors(e.g. conmeds, medical history, lab) in the appropriate eCRF(s) 	Investigator discretion		
^a Resolution is defined as an outcome of one of the following: (1) return to baseline values, (2) stable values at three subsequent monitoring visits at least 2 weeks apart, (3) remain at elevated level after a maximum of 6 months, (4) liver transplantation, and (5) death.				

Table 16-5	Follow up requirements for liver laboratory triggers
------------	--

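### The general restart clause in Protocol Section 9.1.1 is not reconciled with the stricter restart conditions in Table 16-4 after an ALT/AST rise with raised bilirubin or INR

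*Protocol*

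**What the plan says.** Section 9.1.1 of the Protocol lists the events after which study treatment must be discontinued. One group is headed "Unexplained increases in transaminases (ALT or AST) or total bilirubin as follows", and one item in it is "ALT or AST >3x ULN and (total bilirubin >2x ULN or INR >1.5".

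The same section then sets a general restart rule: "Study treatment may be restarted at the discretion of the investigator, if the reason for discontinuation has resolved". It adds: "Every effort should be made to restart study treatment, if deemed appropriate by the investigator". The only express bar attached to that clause is that treatment is not "allowed to be re-started following initiation of prohibited medication that requires study drug discontinuation", with a reference to Table 6-2.

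Appendix 3 (Section 16.3), Table 16-4, has a row for ALT or AST above 3x ULN in participants with normal baseline values, combined with "Total bilirubin > 2 x ULN (or INR > 1.5" (closing bracket omitted). The action is to interrupt study drug, and restart is limited: "Study drug can be restarted only if another etiology is identified and liver enzymes return to" baseline.

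Section 10.2.1 sends the site to Tables 16-4 and 16-5 for the actions required in liver events. For discontinuation of the drug it sends the site to the discontinuation section, that is, to 9.1.1.

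**The concern.** Section 9.1.1 is where the protocol sets mandatory stops and restarts, and it encourages restart where the investigator thinks it appropriate. It cross-refers for other special cases: Table 6-2 for prohibited medication, and Section 6.6.3 for broken treatment codes, where the stop is permanent. For the liver stop it repeats neither of the Table 16-4 conditions and does not mention the table.

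The omitted condition on cause matters most here, because the 9.1.1 trigger is by definition an unexplained rise. At stake is an adolescent whose transaminases rose together with bilirubin or INR, in whom study drug has not been ruled out, and who could be re-dosed because the values came down. Section 4.2 describes an LDL-C effect lasting more than 6 months after a single dose, so the effect of a re-dose cannot be promptly reversed.

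**Working it through.** No arithmetic applies. The check sets the two rules side by side and asks when they give different answers.

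| | Section 9.1.1 | Table 16-4, bilirubin/INR row |
|---|---|---|
| Trigger (normal baseline) | ALT/AST >3x ULN with bilirubin >2x ULN or INR >1.5, unexplained | ALT/AST >3x ULN with bilirubin >2x ULN or INR >1.5 |
| Action | Discontinue (mandatory) | Interrupt |
| Restart | Reason for stopping has resolved; investigator's judgement | Both: a different cause is found, and enzymes are back at baseline |

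**Step 1: same event.** For a participant with normal baseline values the thresholds are identical. For a participant whose ALT or AST was raised at baseline, the table uses multiples of baseline or 300 U/L instead, so the match is exact only for normal baseline values.

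**Step 2: does restart arise under both?** Table 16-4 speaks of interruption and 9.1.1 of discontinuation, which the glossary calls permanent. But 9.1.1 itself allows a discontinuation to be reversed, so the difference in terms does not separate the two rules.

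**Step 3: cases.**
- A different cause is found and enzymes are back at baseline: both rules allow restart.
- Values remain raised: the table does not allow restart, and the reason for stopping under 9.1.1 has not resolved.
- Values are back at baseline and no cause is found: 9.1.1 on its wording allows restart at the investigator's judgement; the table does not.

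The third case is where the rules differ.

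**Step 4: is there a rule of precedence?** Section 10.2.1 names both places and ranks neither. Section 9.1.1 does not cite Table 16-4.

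**Step 5: reach.** The restart text sits directly on the bilirubin/INR row. It may also cover the other interruption rows, including the one with symptoms ("Severe fatigue, nausea, vomiting, right upper quadrant pain"), but the cell borders of that table are not preserved in the text available. The point therefore rests on the bilirubin/INR row.

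**The case against.** The strongest reply is that the safeguard is already in the protocol and in force. Section 10.2.1 makes a standard liver process obligatory and routes these events to Appendix 3. For participants with normal baseline values, Table 16-3 lists both ALT/AST >3x ULN with INR >1.5 and potential Hy's Law cases. A general permission does not cancel a specific restriction, and a site that follows the table breaches nothing in 9.1.1. This stands, and it is why a reader who infers a true contradiction, or a missing safeguard, goes further than the documents allow.

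A second reply is that the reason for stopping is an unexplained rise, so it might not count as resolved until it is explained. That reading is open, but 9.1.1 does not state it, and normalised values are an equally natural meaning of resolved.

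Third, 9.1.1 also requires a stop where participation might put the participant at risk, and restart remains subject to the investigator's judgement. This lowers the risk. It does not supply the limit that Table 16-4 places on that judgement.

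Fourth, there is oversight. Under Section 6.5.2.1, confirmed cases with no alternative cause are reported as SAEs, within 24 hours under Section 10.1.3, and the DMC reviews hepatobiliary events (Section 10.2.3). This makes an unnoticed rechallenge unlikely. But the 6.5.2.1 criteria require bilirubin >2x ULN, so a rise with INR >1.5 alone falls outside them, and reporting is not a restart rule.

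Finally, Section 1.1 reports no increased hepatic risk in adults. That bears on how often the case would arise, not on which rule applies when it does.

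**Conclusion.** The inconsistency is real and narrow. For one mandatory liver stop, Section 9.1.1 and Table 16-4 set different restart conditions, and they give different answers when values normalise without a cause being found. Severity is low: compliance with both is possible by following the table, and Section 10.2.1 already leads there.

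No event rate is given and none is assumed, so no count of affected participants can be stated. The primary analysis is not affected, since the SAP (Section 2.5.1) uses data regardless of treatment discontinuation.

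A reader might also infer that every liver stop in 9.1.1 should carry the Table 16-4 restart conditions. The documents do not support that. The other 9.1.1 liver criteria do not all correspond to an interruption row, and Table 16-5 handles isolated bilirubin rises without such a condition. Nor does the absence of an express restart bar after confirmed anaphylaxis amount to an error, because the general safety stops and the investigator's judgement cover it.

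The conclusion assumes normal baseline values and that the restart text applies at least to the bilirubin/INR row, where it appears.

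**What to change.** Add after the restart sentence in Section 9.1.1: *After a liver event for which Table 16-4 requires interruption (including ALT or AST >3x ULN with total bilirubin >2x ULN or INR >1.5), study treatment may be restarted only when a different cause has been established and liver enzymes are back at baseline. Table 16-4 takes precedence over this section.*

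The wording is tied to events for which the table requires interruption, so it creates no new medical restriction.

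The cost is this addition in an amendment and a notice to sites, with no extra procedures. The downside is that a participant whose values normalise with no cause found stays off study drug, while remaining in follow-up. If dosing has already ended, the useful step is to check whether any such stop was followed by re-dosing.
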